11.0. STATISTICAL PLAN

11.1. Statistical Methods

The study is exploratory and as such descriptive statistics will be used. Continuous variables will be expressed as median values, range of values, and mean \pm standard deviation while categorical variables will be expressed as number (percentage). Qualitative and quantitative differences between subgroups will be analyzed by Chi-square or Fisher's Exact tests for categorical parameters and Student's t test or Mann Whitney test for continuous parameters as appropriate. Statistical significance will be taken as p < 0.05.

11.2. Subject Population(s) for Analysis

18 patients will be enrolled into 3 equally sized groups of 6. This is deemed adequate to delineate whether further studies are warranted based on safety and efficacy observations made.

11.3. Significance

See above section 11.1

11.4. Termination Criteria

Termination of the study requires an assessment of the grade and number of SAEs, as well as their relatedness to the drug. A three point scale will be used for relatedness: unrelated, possibly related, and definitely related. Both sets of parameters are defined in Section 7.3, page 18. Definitely related will be assessed both temporally in relation to vaccine administration and will require the absence of other possible explaining factor(s).

- 1. The study will be terminated if a Grade 4 AE or death occurs that is considered possibly or definitely related to vaccine.
- 2. As previously mentioned in Section 7.4, page 19, a hold will be placed on further enrollment into a group if a patient develops a Grade 3 or SAE that is considered to be definitely related to vaccine. If this occurs, the study will be terminated if a second patient in a different group subsequently develops a grade 3 AE or SAE that is considered to be definitely related. All patients will continue to be followed for at least 52 weeks after the last dose of vaccine to collect additional safety data.
- 3. In the absence of a previous clinical hold on enrollment in any group, the study will be terminated if at any time *two patients*, *one each from different groups*, *concurrently develop* a Grade 3 AE or SAE both of which are considered definitely related. Such patients will continue to be followed for at least 52 weeks after the last dose of vaccine to collect additional safety data.

11.5. Accountability Procedure

All vaccine vials will be accountable in hard copy listings by the clinical coordinator using standardized good clinical practice procedures.

11.6. Deviation Reporting

Not applicable due to exploratory nature of the study

12.0. DIRECT ACCESS TO SOURCE DATA/DOCUMENTATION

Periodic audits by vaccine manufacturer will be allowed if this is thought to be needed. This will be formalized in a written agreement between Baylor Scott and White and Dynavax Technologies.

13.0. QUALITY CONTROL AND QUALITY ASSURANCE

Yearly submission of the findings of the study relevant to patient safety and overall study progress is required by the IRB. Annual reports to the FDA, including any pertinent case summaries, will be submitted under this IND # 18850 as required by 21CFR312.33. The data on each participant will be recorded in separate patient binders to which only the principal investigator and study coordinator have access. Also, periodic data monitoring will be conducted by an independent department through Baylor Scott and White Research Institute.

14.0. ETHICAL CONSIDERATIONS

This study will be conducted according to US and international standards of Good Clinical Practice (FDA regulations 21 CFR 312 for IND studies and FDA guidance E6) for all studies.

All subjects for this study will be provided a consent form describing this study and providing sufficient information for subjects to make an informed decision about their participation in this study. This consent form will be submitted with the protocol for review and approval by the IRB. The formal consent of a subject, using the IRB-approved consent form, will be obtained before that subject is submitted to any study procedure. This consent form must be signed by the subject or legally acceptable surrogate, and the investigator-designated research professional obtaining the consent.

15.0. DATA HANDLING AND RECORD KEEPING

Study binders for each patient kept in locked coordinator office. Weekly review of all safety data by the principal investigator.

16.0. PUBLICATION PLAN

[figure not shown]
This will be specified in written form by Baylor Scott and White Research Institute.

^{** 5%} of recipients of anti-HBc donor liver are anticipated to be anti-HBc positive. These patients will be excluded if anti-HBs also > 20 mIU/ml. Patients transplanted for HBV infection are anticipated to be anti-HBc positive

[#] If anti-HBs level remains < 10 mIU/ml

TABLE 1. Study Participation Table

	Visit 1: Screening	Visit 2 Enrollment/ Baseline	Visit 3 4 Week Follow up (+/- 3-5 d)	Visit 4 8 Week Follow up (+/- 3-5 d)	Visit 5: 12 Week Follow Up (+/- 3-5 d)	Visit 6: 24 Week Follow Up (+/- 1 week)	Visit 7: 60 Week Follow Up (+/- 1 week)
Read and Sign Informed Consent	Х						
Medical History	Х						Х
Review of Immunosuppresants	Х	Х	Х	Х	Х	Х	Х
Interview, brief physical	Х	Х	Х	Х	Х	Х	Х
Vital Signs (heart rate, blood pressure, temperature)	Х	Х	Х	Х	Х	Х	Х
Missing HBV blood testing*	Х						
Quant anti-HBs	X [≠]	Х	Х	Х	Х	Х	Х
CRP**		Х	Х	Х	Х	Х	Х
Pregnancy test [¥]	Х	Х	Х		Х	X _∞	
Hepatic function panel		Х	Х	Х	Х	Х	Х
Patient Related Outcome Form for Inflammatory Disorder		Х	Х	Х	Х	Х	Х
Repository Blood Sample (for repeat antibody test)		Х	Х	Х	Х	Х	Х
Vaccine Administration, with observation for reactions		Х	Х		X***		
Adverse effects form [±]			Х	Х	Х	Х	Х

^{*} Test for anti-HBs, anti-HBc, or HBsAg if not in the medical record or > one year previously. Test for HIV and HCV antibody is not within 4 months of screening.

[≠] Only done at this visit if medical record indicates patient is anti-HBs positive by qualitative testing.

^{**} This will only be done in patients taking TNF or interleukin inhibitor therapy for chronic inflammatory disorders.

[¥] If potentially child bearing female. Patients who are positive will not be eligible.

^{***} A 3rd dose will be offered to those participants who lack seroprotection (>10 mIU/ml) at week 8.

[±] Observation for adverse events includes weekly telephone calls for 4 weeks after each vaccine dose.

 $[\]infty$ If patient requires third dose of vaccine as per protocol.

Appendix 1. Form to Capture All Adverse Events

Participant Number	Date	Visit Number

System Involved	Description of Event	HHS* Grade	Unexpect Yes	ted** No	Relatedness a. Unrelated b. Possibly c. Definitely	Time Relationship to Dose 1	Time Relationship to Dose 2	MAAE, pIMMC, and/or SAE (specify) Yes No	Type Intervention	Participant Withdrawal Needed Yes No	Time to Resolution	PI Initials & Date
Local reaction												
Vital Signs												
Systemic												
Lab Abnormality												
HEENT												
Cardiac												
Lung												
Abdomen												
Muscular/ skeletal												
Neuro												
Skin												
Other												

Footnotes to Appendix 1

*As defined in Common Terminology Criteria for Adverse Events (CTCAE). Version 5.0, November 27, 2017). U.S. Department of Health and Human Services/National Institute of Health/National Cancer Institute

Grade 1: mild, asymptomatic or mild symptoms; clinical or diagnostic observations only; intervention not needed.

Grade 2: Moderate; minimal local or noninvasive intervention indicated.

Grade 3: Severe or medically significant but not immediately life threatening; hospitalization or prolongation of hospitalization indicated; disabling; limiting self-care

Grade 4: Life threatening; urgent intervention needed

Grade 5: Death related to AE.

^{**} Unexpected indicates that the adverse event if not listed in the investigator's brochure or is not listed at the specificity or severity observed as indicated in CFR 312.32. Revised as of April 1, 2018.

Appendix 2 A. Psoriasis Patient Related Outcome Measurement [Data Collected at Each Study Visit]

Patient Study	v Number	Date	Visit Number	Visit in Between Those Specified?	Yes	No

Skin related						
Areas affected	Arms	Legs	Back	Neck	Scalp	Feet
New areas Since last visit	YES/NO	Arms Legs	Back	Neck	Scalp	Feet
Eye	Redness	Pain	Sensitivity to light	Blurred vision		
Joint related	YES/NO	If so, where? (see below)				
	Fingers	Back	Neck	Shoulder	Hips	Ankles
Systemic						
Fever or feeling feverish?	YES/NO	99-100 F	101-103 F	>103 F		
Fatigue	YES/NO	Minimal	Moderate	Severe		
Overall assessment*	No change	Feel slightly worse	Feel moderately worse	Feel much worse		

Comments	 	

Appendix 2B. Rheumatoid Arthritis/Ankylosing Spondylitis Patient Related Outcome Measurement [Data Collected at Each Study Visit]

Patient Study Number Visit in Between Those Specified?-- Yes Date Visit Number No Joint related Number affected < 2 ≥ 5 ≥2,≤5 Location Hands Wrists **Elbows** Shoulder Hips Ankles On a scale 1-10 (with **Joint Pain** On a scale 1-10 (with On a scale 1-10 (with 10 being the worst) 1 2 3 4 5 6 7 8 9 10 1 2 3 4 5 6 7 8 9 10 1 2 3 4 5 6 7 8 9 10 1 2 3 4 5 6 7 8 9 10 1 2 3 4 5 6 7 8 9 10 1 2 3 4 5 6 7 8 9 10 Stiffness Mild Moderate Severe **Swelling** Mild Moderate None Severe If so, where? (see **New joint** YES/NO location below) **Elbows** Shoulder Hands Wrists Hips Ankles Systemic YES/NO Fever or feeling 99-101 F > 101-103 F >103 F feverish? Muscle aching YES/NO If so, where? **Fatigue** YES/NO Minimal Moderate Severe Feel slightly worse Overall No change Feel moderately Feel much worse assessment* worse **Function related** Difficulty with YES/NO Minimal Moderate Severe dressing Difficulty with YES/NO Minimal Moderate Severe driving YES/NO Difficulty with Minimal Moderate Severe grasping Difficulty with YES/NO Moderate Minimal Severe

walking

Appendix 2 C. Inflammatory Bowel Disease Patient Related Outcome Measurement [Data Collected at Each Study Visit]

Patient Study Number _____ Date _____ Visit Number ____ Visit in Between Those Specified?-- Yes No

Bowel related					
Number stools/ 24 hr	< 2	>2 but < 5	>5		
Blood in stools	None	Occasional (1-3 times Weekly)	Most days (4-6)	Daily	
Amount		Minimal	Moderate	Severe	
of blood		(teaspoonful mixed with stool)	(More than teaspoonful, but less than cupful)	(Cupful or more)	
Abdominal Pain	None	On a scale 1-10 (with 10 being the worst) 1 2 3 4 5 6 7 8 9 10	On a scale 1-10 (with 10 being the worst) 1 2 3 4 5 6 7 8 9 10	On a scale 1-10 (with 10 being the worst) 1 2 3 4 5 6 7 8 9 10	
Systemic					
Fever	YES/NO	99-101 F	> 101 to 103 F	> 103	
Fatigue	YES/NO	Minimal	Moderate	Severe	
Overall assessment*	No change	Feel slightly worse	Feel moderately worse	Feel much worse	
Social Function					
	Normal	Occasional limitation	Several times weekly	Absence from work	Home ridden
Food tolerability	No problem	Minimally affected	Moderately affected	Severely affected	

Comments	 	 	

Appendix 3. Quick View Table of Criteria for Subject Withdrawal, Vaccine Withdrawal, and Study Termination

Adverse Event	Relatedness	Subject	Vaccine	Anticipated Follow up	Study Termination
	Not Poss Def	withdrawal	Withdrawal		
Death	Not	-	-	-	No*
	Possibly	-	-	-	Yes
	Definitely	-	-	-	Yes
Grade 4	No	No	No	Until 52 weeks after last vaccine dose	No*
	Possibly	Yes	Yes	Until 52 weeks after last vaccine dose	Yes
	Definitely	Yes	Yes	Until 52 weeks after last vaccine dose	Yes
Worsened underlying	Regardless of	Yes	Yes	Until 52 weeks after last vaccine dose	No, but hold on further enrollment & vac-
disease in Group A patient	relatedness				cine in group A if AE is definitely related**
	Not	No	No	Until 52 weeks after last vaccine dose	No
	Possibly	No***	Yes	Until 52 weeks after last vaccine dose	No
Grade 3 AE or SAE in any	Definitely	No***	Yes	Until 52 weeks after last vaccine dose	Yes, if a second patient in different group
patient group					has a Grade 3 AE or SAE that is also
					definitely related to vaccine $^{\Omega}$ If this does
					not occur, a hold on further enrollment &
					vaccine in the group the patient belongs to
Liver allograft rejection	Possibly	No***	Yes	Until 52 weeks after last vaccine dose	No
	Definitely	No***	Yes	Until 52 weeks after last vaccine dose	Yes, if a second patient in different group
					has a Grade 3 AE or SAE that is also
					definitely related to vaccine $^{\Omega}$ If this does
					not occur, a hold on further enrollment &
					vaccine in group C will be enacted.

^{*}The finding of a death or Grade 4 AE that is considered unrelated to vaccine will not be considered sufficient to terminate the study nor place a hold on further enrollment in that group.

^{**}The finding of a Grade 3 AE or SAE that is considered definitely related to vaccine will place a hold on further enrollment in Group A and all other groups (B and C). Should two subjects in one group have the same or similar Grade 3 AE or SAE assessed as *possibly* related, then enrollment and vaccination in that group will also be put on hold.

^{***} If patient meets criteria for vaccine withdrawal they will still be followed for safety until week 60.

 $^{^{\}Omega}$ Study termination will occur if two patients, one each from two different groups, develop a Grade 3 AE or SAE considered to be definitely related to vaccine.

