7.3 Vaccine Withdrawal

Need for vaccine withdrawal and subject withdrawal (see Section 7.4 below) will be assessed by application of the grading criteria for adverse events as described in the Common Terminology Criteria for Adverse Events as published by the US Department of Health and Human Services/National Institutes of Health, and the National Cancer Institute (version 5.0, November 2017). A three point scale will be used to judge relatedness: unrelated, possibly related, and definitely related. *Possibly related* will be defined as any AE in which there is a reasonable time sequence to vaccination but the AE could be explained by another potential cause such as other drugs or events, patient noncompliance with immune suppression medication, or recent switch in immune suppression medication. Definitely related will require a plausible time relationship to vaccine administration that cannot be explainable by other events and condition as described above. Also, it will be further considered to be definitely related if there is a response to withholding further vaccination.

1. Any patient in Group A who is deemed to have significant clinical worsening of their inflammatory disorder or develop a new onset pIMMC after one or two doses of vaccine will be withdrawn from further dosing regardless of relatedness to the vaccine. However, the subject will be followed until week 60 to collect additional safety data. During this time, additional immunogenicity data may be obtained if the patient had received at least two doses of vaccine

before clinical worsening became apparent and if seroprotective levels were observed when last tested.

2. Regardless of which group a patient belongs to, any subject who has a Grade 3 AE or SAE will not receive further vaccination if the adverse event is considered to be possibly or definitely related to Heplisav-B. Each of these patients will continue to be seen at the visits specified in the protocol until the end of the study (week 60) so that additional safety data may be collected.

Additional immunogenicity data may be obtained if the patient had received two doses of vaccine before the AE became apparent and if seroprotective levels of anti-HBs were evident when last tested.

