7.4 Clinical Hold on Further Group Enrollment

- 1. If at any time a Grade 3 AE or SAE develops that is considered to be definitely related to vaccination, then an immediate hold on further enrollment will be placed on the group the patient belongs to. Also, neither the affected individual nor other participants in that group will be given further vaccine inoculations. This applies to all groups.
- 2. If transplant rejection develops that is considered to be definitely related to vaccination, this will be considered as an SAE that is medically attended (MAAE) and a clinical hold on further enrollment will be enacted for the group (C) the patient belongs to. In addition, no further vaccination will be given to the affected individual.
- 3. Should 2 patients in any group have a grade 3 AE or SAE considered to be *possibly* related to vaccine, then an immediate hold on both further enrollment and repeat inoculations in that group will be enacted.

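### The Appendix 3 footnote states two enrolment and dosing hold rules differently from Section 7.4, and its version of the two-patient trigger is less protective

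*Protocol*

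**What the plan says.** **Two possibly related events in one group.** Section 7.4 item 3 sets the trigger as "Should 2 patients in any group have a grade 3 AE or SAE considered to be" possibly related, and the action as "then an immediate hold on both further enrollment and repeat inoculations in that group will be enacted". It puts no condition on the type of event. The double-asterisk footnote to Appendix 3 reads "Should two subjects in one group have the same or similar Grade 3 AE or SAE assessed as" possibly related, and then holds enrolment and vaccination in that group. The protocol does not define similarity.

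**One definitely related event.** Section 7.4 item 1 says "then an immediate hold on further enrollment will be placed on the group the patient belongs to". Section 11.4 item 2 agrees: "a hold will be placed on further enrollment into a group if a patient develops a Grade 3 or SAE" judged definitely related. The Appendix 3 table row for a definitely related Grade 3 AE or SAE also limits the hold to enrolment and "vaccine in the group the patient belongs to". The footnote to the same table says that such an event, definitely "related to vaccine will place a hold on further enrollment in Group A and all other groups (B and C".

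**The affected patients.** Under Section 7.3 item 2, a patient with a Grade 3 AE or SAE "will not receive further vaccination if the adverse event is considered to be possibly or definitely related to Heplisav-B". This is the same whichever hold rule is used.

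**The concern.** Safety is a co-primary objective, and the hold rules are the protocol's means of protecting the other patients in a group once some have been harmed. The two-patient rule exists in two versions that give different decisions on the same facts. If one patient has a possibly related Grade 3 neurological event and another in the same group a possibly related Grade 3 hepatic event, Section 7.4 stops the group and the footnote does not.

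Appendix 3 does not correct itself. Its row for a possibly related Grade 3 AE or SAE answers no to study termination and mentions no hold, and the row for possibly related rejection does the same. The double-asterisk marker appears only on the Group A disease-worsening row. A reader of the quick-view page therefore meets the two-patient rule only in its weaker form, and no statement gives the main text precedence over the appendix.

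The scope wording is a lesser matter. It would close enrolment in groups that Section 7.4 leaves open.

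**Working it through.** The protocol gives no operating characteristics for these rules, so there is no stated figure to reproduce. The check is a comparison of the texts, a dose count that needs no risk assumption, and an illustration that does.

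**1. Comparison**

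| Situation | Section 7.4 | Section 11.4 item 2 | Appendix 3 table | Appendix 3 footnote |
|---|---|---|---|---|
| Two possibly related Grade 3 AEs/SAEs in a group, alike | Hold group | Not addressed | No hold mentioned | Hold group |
| Two such events, unlike | Hold group | Not addressed | No hold mentioned | No hold stated |
| One definitely related Grade 3 AE/SAE | Hold that group | Hold that group | Hold that group | Literally, enrolment hold in A, B and C |

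The second and third rows conflict.

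**2. Doses at stake on the trigger**

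Inputs: 6 patients per group (Section 11.2); doses at baseline and week 4, and at week 12 if not seroprotected at week 8 (Section 4.7); the two affected patients already off vaccine (Section 7.3 item 2). That leaves 6 − 2 = 4 patients.

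- All 4 have had dose 1 only: 4 × 2 = 8 further doses at most.
- None of the 4 has enrolled: 4 × 3 = 12 doses at most.

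These are ceilings. They require both events to occur before any of the 4 has dose 2, and all 4 to need the week 12 dose.

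**3. Illustration of how often the rules differ**

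Assumptions, none from the protocol: independent per-patient risk q of a possibly related Grade 3 AE or SAE, and k equally likely event types, with two events counted as similar only if they are of the same type.

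Section 7.4 item 3: P(hold) = 1 − (1−q)^6 − 6q(1−q)^5. At q = 0.2 this is 1 − 0.2621 − 0.3932 = 0.3446.

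Footnote: P(hold) = 1 − Σ C(6,m) q^m (1−q)^(6−m) × k!/[(k−m)! k^m], summed over m from 0 to 6, with terms for m > k equal to 0. At q = 0.2 and k = 3, the binomial probabilities for m = 0 and 1 sum to 0.6554, and those for m = 2 and 3 are 0.2458 and 0.0819. The chances of no match are 1, 1, 6/9 and 6/27. The result is 1 − (0.6554 + 0.1638 + 0.0182) = 0.1626.

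| Assumed risk q | Section 7.4 | Footnote, k = 2 | k = 3 | k = 5 |
|---|---|---|---|---|
| 0.10 | 11.4% | 6.5% | 4.5% | 2.8% |
| 0.20 | 34.5% | 22.2% | 16.3% | 10.6% |
| 0.30 | 58.0% | 41.8% | 32.3% | 22.0% |

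A finer classification widens the gap. With k = 12 the footnote's chance of a hold is 1.2%, 4.7% and 10.3% at the same three risks.

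**4. Scope**

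The footnote's all-group wording covers enrolment only. It can affect only patients not yet enrolled in the other two groups: 0 to 2 × 6 = 12, depending on recruitment at the time. It changes no enrolled patient's dosing.

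**The case against.** The best defence is that the two texts can be followed together. The footnote does not say that a hold occurs only when the events are alike, Section 7.4 item 3 covers every case the footnote covers, and Section 11.4 refers back to Section 7.4 for holds. Appendix 3 is a summary of withdrawal and termination criteria, and the answer of no for possibly related events sits in the termination column. Other safeguards also remain: weekly safety review by the principal investigator, prompt reporting of Grade 3 and 4 events, the investigator's discretion to withhold doses, and study termination for a possibly related Grade 4 event or death.

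Much of this stands as a limit on the harm. A team that works from Section 7.4 will act correctly, and the risk arises when the quick-view page is used alone. But that is the purpose of such a page, and a summary that adds a condition to a stopping rule misstates it.

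On scope, the footnote may be a clumsy way of saying that the group-level rule applies to each of A, B and C, as the last sentence of Section 7.4 item 1 does. That reading is plausible, and the literal one errs towards caution. The words still contradict the table they annotate.

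The percentages rest on assumed risks and an assumed number of event types, and the protocol supports neither. They show direction and possible size only. The contradiction does not depend on them.

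**Conclusion.** The point holds. The footnote adds a similarity condition that Section 7.4 item 3 does not contain, so two unlike possibly related Grade 3 events would leave a group open on the footnote's wording when the main text closes it. The exposure is limited to the 4 unaffected patients in the group, with ceilings of 8 or 12 doses. Under the assumed risks of 10% to 30% and 2 to 5 event types, the footnote's chance of a hold is between about a quarter (2.8/11.4 = 0.25) and about seven tenths (41.8/58.0 = 0.72) of the Section 7.4 value.

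The scope conflict is also real as worded, but secondary: it concerns enrolment only, errs on the safe side and may be a drafting slip. Both should be corrected. Neither affects the design or the analysis. The conclusion takes Section 7.4 as the intended rule, which on scope Section 11.4 and the table body support; on the trigger it is the more protective text.

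**What to change.** Amend the double-asterisk footnote to Appendix 3:

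- Delete the words that require the two events to be the same or similar, so that any two possibly related Grade 3 AEs or SAEs in a group trigger the hold.
- Replace the reference to Group A and all other groups with the affected patient's own group, and say that this rule applies to Groups A, B and C alike.
- Add the two-patient hold, or the footnote marker, to the rows for possibly related Grade 3 AE or SAE and for possibly related rejection.

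A line stating that Sections 7.3 to 7.5 and 11.4 prevail over Appendix 3 would guard against similar slips, but it is optional. If the sponsor in fact intends the footnote's version, Section 7.4 should be changed instead and similarity defined.

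The cost is a wording correction to one footnote and its markers, with no added patients, visits or analyses.
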